10.6 Determination of Relationship to Device and/or Procedure

The determination whether the AE is related to the device and/or procedure will be based upon whether a causal relationship between the device or procedure and the AE a reasonable possibility is, *i.e.*, the relationship cannot be ruled out. A causal relationship cannot be ruled out if, in the medical judgement of the Investigator, the effect follows a reasonable temporal association with the use of the device and/or is confirmed by the improvement of the effect upon discontinuation of the clinical use of the device, and/or the effect is not reasonably explained by the Subject’s clinical state.

Device related AEs will be reviewed by DePuy Synthes and reported, if applicable, to the appropriate regulatory body.

10.7 Minimization of Risk

Only trained orthopaedic surgeons with expertise in treating total hip conditions will participate in this study.

Investigators should refer to the instructions for use (package insert, **Exhibit H**) for additional information and reference the surgical technique (**Exhibit D**).

The Sponsor will further minimize the identified and/or emergent risks throughout the study, by reviewing the reported complications and adverse effects. All AEs, SAEs, ADEs, SADEs and UADEs will be reviewed and evaluated by the Medical Monitor assigned to this study.

11 STUDY SUMMARY STATEMENT

In summary, this PMA Post-Approval Study for the 36 mm CERAMAX® Ceramic Hip System will support short and mid-term safety and performance with an expanded pool of clinical investigators. The newly enrolled subjects will expand information contained in the original PMA submission by supporting survivorship at 5 years post-op.

For a given subject, their study participation will end if they withdraw consent, as per PI decision, undergo a revision of either the acetabular shell and/or liner, are reported as deceased or when they have reached the final endpoint at 5 years.

12 IMPLANTS RETRIEVALS

Any prosthesis that may be made available because of a removal or revision surgery or subject death will be submitted for detailed evaluation. A protocol for device explanation and retrieval analysis is included (**Exhibit M**).

If the implant is known to be available, the sponsor will encourage the investigator to preserve the prosthesis alone, or, in the event of a death, if possible, provide the excised hip joint with the implant in place.

Retrieval analysis will be completed by one or more independent reviewers as outlined in the **Exhibit M**. In addition, DePuy Synthes and/or CeramTec may perform analyses, as appropriate.

13 CLINICAL MONITORING

Monitoring activities will follow the Sponsor standard operating procedures (SOPs), applicable FDA regulations and good clinical practices (GCPs). Given that this is a regulated study and the level of risk to Subject safety and data integrity, and criticality of ensuring compliance, monitoring will include onsite monitoring visits. Remote monitoring may be conducted if deemed appropriate by the Clinical Study Lead and Clinical Operations lead (e.g., if sites have not enrolled (consented) any Subjects).

14 REPORTING

Reports of this study will be prepared according to the Guidance for Industry and FDA Staff: Clinical Data Presentations for Orthopaedic Device Applications.

Per the Guidance for Industry and FDA Staff- Procedures for Handling Post-Approval Studies Imposed by PMA Order

<http://www.fda.gov/downloads/MedicalDevices/DeviceRegulationandGuidance/GuidanceDocuments/ucm071013.pdf>), the applicant will provide a report to the FDA every 6 months for the first 2 years following device approval and annually thereafter until the end of the study (see **Section 16.2**).

The reports will include:

- A complete listing of all sites and IRBs.
- Enrollment updates (during enrollment) – screening/recruitment logs from all sites
- Site follow-up compliance to clinical investigation plan,
- Clinical Results- Overall Harris Hip Scores and Harris Hip sub-scores (pain, function, activity, deformity, and range of motion)
- Radiographic Results
- Safety Summary- documentation and compilation of all adverse events
- Survivorship at each year post-operatively for which there are sufficient subjects to compute survivorship

15 PUBLICATION POLICY

All manuscripts of data obtained from this clinical investigation will be reviewed and approved by the sponsor, and each author, prior to any submission. And, current and applicable Medical Device & Diagnostic (MD&D) Publication Policy will be followed.

DePuy Synthes will require a written agreement for any external author(s) prior to initiating any publication. All authors must disclose financial or personal affiliations that could be considered a conflict of interest.

16 PROJECTED TIMELINES FOR POST APPROVAL STUDY

16.1 Overall Study Projected Timeline

The anticipated duration of this investigation is approximately seven years from the time of study initiation.

- It may take up to a minimum of 2 years from the time of study initiation to enroll new subjects.
- Each subject will be followed until they have completed their minimum 5 year follow-up.

All timeline information is reflected as “deltas” compared to previous column.

Expected # of Study Sites	*Expected Date of Study Initiation	Expected Date of Obtaining IRB Approval for all Sites	Expected Date of Completion of Subject Enrollment**	Final Endpoint
Up to 15 (up to 5 original IDE + up to 10 new sites)	6 months after agency approval of PMA	+ 3-6 months	+ 24 months	+ 5 years

* Defined as submission for approval of study by a reviewing IRB

** It is anticipated that it will take up to a minimum of 24 months to enroll new subjects. Approximately 7 subjects will be enrolled monthly.

16.2 Annual/Interim Reports Projected Timeline

Interim Reports will be provided to FDA every six months for two years following the date of final PMA approval. Reports will then be submitted annually until completion of the post-approval study. The contents of the reports are described above in **Section 14**. The schedule of dates for the reports to be provided is noted in the following table:

INTERIM / ANNUAL REPORT DUE DATES (based on April 2, 2013 PMA approval)	
	October 2, 2013
	April 2, 2014
	October 2, 2014
	April 2, 2015
	April 2, 2016
	April 2, 2017
	April 2, 2018
	April 2, 2019
	April 2, 2020
Annual Interim Reports to continue as required, based on 5-year follow-up Final Report will follow FDA reporting requirements

	8.9 Additional Endpoint Analyses	10
9	Data Monitoring Committee (DMC)	10
10	Appendix: Tables, Listings and Graphs Shells	11
11	Reference(s)	11

1 Study Design

This is a prospective, non-controlled, non-randomized, multicenter study of the 36 mm Ceramic on Ceramic (COC) device.

A new enrollment cohort of a minimum of 170 subjects will be prospectively enrolled into the study. Study sites will be comprised of both IDE study sites, as well as newly recruited sites. These subjects will be seen for a pre-op clinic visit at the time of consent, and then at 6 weeks, 1 year, 2 years, 3 years, 4 years, and a minimum of 5 years. The purpose of the pre-op visit will be to obtain patient medical history and baseline information. At the post-op clinic visits the following information will be obtained: a Harris Hip evaluation, radiographic evaluation, subject evaluation and adverse event information (if applicable). The primary endpoint in this study is device survivorship at 5 years post-op. A minimum of 80% of enrolled subjects will be confirmed to either have a surviving implant or to have had a revision at a minimum of 5 years post-op with a clinical evaluation.

For a given Subject, their study participation will end if they withdraw consent, as per Principle Investigator (PI) decision, undergo a revision of either the acetabular shell and/or liner, are reported as deceased or when they have reached the final endpoint at 5 years.

2 Treatment Assignment

Treatment assignment in this study was not randomized. All subjects received the 36mm COC device, and this was the only device configuration of interest in this PAS. Details regarding sample size are presented in Section 8.

3 Randomization and Blinding Procedures

This was a non-randomized, open-label study, and the sponsor was not blinded to any part of the study or data at any time during the study.

4 Interval Windows

The study includes the following time periods: Pre-op, 6 Wk, 1 Yr, 2 Yr, 3 Yr, 4 Yr, and 5 Yr Min. Intervals related to each are shown in Table 4-1 below.

Table 4-1 Interval Windows for Study Visits

Visit	Mininum Day	Maximum Day
Pre-op	-90 (-180 for Radiographic Data)	0
6 Weeks (Optional)	1	92
1 Yr	275	455
2 Yr	640	820
3 Yr	1005	1185
4 Yr	1370	1550
5 Yr Min	1825	2555

Time point specific data which were collected for the primary and secondary efficacy-related objectives will be assessed for compliance with these intervals. Only data which can be attributed to the Visit intervals in Table 4-1 will be used in the analysis of primary and secondary endpoints. If multiple measurements fall into the specified windows, the last value within the window will be utilized for analysis.

5 Levels of Significance

There are no pre-specified hypotheses and all analyses are exploratory. Summaries of the primary and secondary endpoints in this study are being undertaken without established statistical power. Any p-values and confidence intervals which are provided are only intended to facilitate clinical judgement.

6 Analysis Sets

There is only one analysis set defined for this study:

Safety Analysis Set - Subjects are considered to be in this analysis set if they have provided informed consent and treated as indicated in the protocol.

All analyses will be conducted on the Safety Analysis Set.

7 Sample Size Justification

The sample size will be a minimum of 170 prospectively enrolled subjects. This sample size will provide data upon which to obtain a 5-year survivorship estimate from newly enrolled subjects who did not participate in the COC36 IDE study. The sample size of 170 subjects in this PAS is approximately the same sample size of COC36 IDE investigational subjects, and hence will provide sufficient data on a new cohort of subjects to further support mid-term clinical success.

The objective of this study is to obtain an estimate of device survivorship at 5-years post-operatively. The 170 enrolled subjects will provide a minimum of 136 subjects (80% of enrolled subjects) with 5-year follow-up. This will yield a 5-year survivorship estimate that has an approximate 3.6% margin of error. In particular, Peto's estimate¹ for the variance of a Kaplan-Meier survival estimate is

$$var(\hat{S}(t)) = \frac{(\hat{S}(t))^2(1 - \hat{S}(t))}{n(t)}$$

where $\hat{S}(t)$ is the estimate of survival at time t and $n(t)$ is the number of unrevised subjects at risk (still being followed) at time, and t . Hence, if it is assumed that the point estimate of survival is at a minimally acceptable level of 95.1% for subjects in this PAS, and there is a minimum of 136 subjects (80% of enrolled subjects) at 5-years post-operatively upon which this estimate is based, then an estimate for the variance of the Kaplan-Meier survival estimate at 5 years is

$$var[\hat{S}(5)] = \frac{[0.951]^2(0.049)}{136} = 0.00034,$$

and a two-sided 95% confidence interval margin of error for survival at 5 years is anticipated to be approximately

$$1.96 * \sqrt{0.00034} = 3.6\%.$$

A sample size of 170 enrolled subjects is therefore justified in order to obtain a 3.6% margin of error on a 5 year survivorship estimate.

8 Statistical Analysis Methods

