8.6 Treatment Assignment

The 36 mm COC device is the only device configuration of interest in the study.

¹ Cantor, A. Estimates of the Variance of the Kaplan-Meier Estimator. In: *Extending SAS® Survival Analysis Techniques for Medical Research*. 2nd ed., Cary NC: SAS Institute, 2003:24.

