8.11 Informed Patient Consent (IPC) and Authorization for Release of Medical Records

An informed patient consent must be obtained for all subjects in person prior to enrollment into this 36 mm COC Post-Approval Study. Subjects who agree to participate will complete an IRB-approved IPC that documents his or her willingness to take part in this post-approval study. Each potential subject will have the nature and the purpose of this clinical investigation explained to him or her by the Clinical Investigator or another member of the investigative team at the site. The investigator will explain the following features of the study to the patient thoroughly and will offer to answer any questions the patient may have.

- The purpose of the study
- Possibility of failure and subsequent treatment(s)
- Alternative procedures
- Requirements of the study (follow-up visits)
- The plan to perform retrieval analysis in the event of an explanted device
- A modest payment may be provided to cover subject travel expenditures associated with study participation to 5-years.

Prior to entry into this clinical investigation the patient must give voluntary, written informed patient consent to participate by signing the IPC. A copy of the IPC is to be provided to the subject. A study subject is enrolled once they have signed the IPC and had the study device implanted.

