9 POST APPROVAL STUDY PLAN

9.1 Subject Population

For the purpose of this study, a Subject is defined as an individual who participates in the clinical study as a recipient of the investigational product. Note: before the IPC is obtained, a Subject is referred to as a “patient”.

The post-approval study (PAS) will be comprised of:	Prospectively enrolled subjects in this COC36 PAS study who meet the eligibility criteria described below and are willing to provide written informed consent.
---	--

The Investigator or designee will solicit the IPC of any patient meeting the eligibility criteria and will explain the features of the study and answer any questions from the patient.

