9.7 Enrollment & Subject Identification Number

A study subject is **enrolled** when they have met eligibility criteria, been consented and had the THA procedure and study device implanted per protocol. Once enrolled, the site assigns the subject ID number which is comprised of a two-digit site code followed by a 4- digit subject specific code. For example, the first three enrolled subjects at site #06 would be: 06-0401, 06-0402, 06-0403.

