Interim Visits	
An interim office visit is defined as any visit at the study site where a study Subject is seen by one of the site staff including the Principal Investigator (PI), any sub-investigator (as appropriate), and anyone identified on the PI's team, outside of the scheduled study visit. An interim visit is only to be reported when the visit falls between study intervals as described in Table 4. An Interim Visit CRF is not to be completed if the Subject comes in for additional, unplanned visits in the "in-window" study interval.
 
If the previous protocol-defined, study interval visit was missed, the required CRFs in that previously-missed interval visit are also required along with the Interim Visit CRF.
 
If the interim visit is related to a new, worsening, or resolved adverse event, both an Adverse Event CRF and Interim Visit CRF are completed.

End of Study/ Withdrawal	
This form must be completed for all enrolled subjects to either reflect
 
 • Completion of final endpoint (Minimum 5 years) • Premature withdrawal 
Study participation may be prematurely discontinued through revision of acetabular components (shell and/or liner), withdrawal of consent, or death.
 
➤ NOTE: A revision is defined as a surgical procedure of the affected hip where one or more of the THA components (femoral stem, femoral head, acetabular shell and/or acetabular liner) are removed. Of note, if both the acetabular shell and ceramic liner remain intact, the Subject will continue to be followed in the study.
 
➤ NOTE: Should it be necessary for the Subject to undergo a revision of either the acetabular shell and/or the acetabular liner between the date of the enrollment and the completion of the study data acquisition, the Subject is withdrawn from study participation. Thus, both an Adverse Event (AE) CRF and an END of Study/Withdrawal CRF would be completed.

Electronic Case Report Forms (CRFs) entered into an electronic data capture (EDC) system will be used to collect all Subject data once a Subject is enrolled in the study. Study sites will be instructed to enter Subject data on to the CRFs via the EDC web-based database portal.

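### Could the SAP's only analysis set leave out implanted subjects because of protocol deviations?

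*SAP*

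**What the plan says.** SAP section 6 sets membership by consent and treatment: "Subjects are considered to be in this analysis set if they have provided informed consent and treated as indicated in the protocol". It then adds: "All analyses will be conducted on the Safety Analysis Set". There is no second set and no rule for protocol deviations.

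The protocol states enrolment twice. Section 8.11, on consent, says: "A study subject is enrolled once they have signed the IPC and had the study device implanted". Section 9.7 says a subject is enrolled "when they have met eligibility criteria, been consented and had the THA procedure and study device implanted per protocol", and has the site assign the subject number at that point. Section 9.8 says electronic case report forms "will be used to collect all Subject data once a Subject is enrolled in the study".

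Other places bear on what treatment means here. SAP section 2 says: "All subjects received the 36mm COC device, and this was the only device configuration of interest in this PAS". Protocol 8.6 says: "The 36 mm COC device is the only device configuration of interest in the study". In Protocol 9.1, "a Subject is defined as an individual who participates in the clinical study as a recipient of the investigational product".

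**The concern.** The treatment condition in SAP section 6 can be read as a per-protocol filter under a safety label. Protocol section 7 rules out the direct anterior approach and 7.5 limits the stems, so a consented, implanted subject could breach either rule, or be found ineligible after surgery. That subject is enrolled under 8.11 but arguably not under 9.7. Because subject numbers and electronic data both follow enrolment, a strict reading of 9.7 would act before the analysis set is formed.

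One set carries both the survivorship estimate and the adverse event percentages. If the subjects left out were revised more often than the rest, survivorship would look too good. Protocol 8.3 compares the point estimate with 95.1%, so a shift near that level could change how the result is described.

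**Working it through.** **The passages side by side**

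| Place | Condition stated |
|---|---|
| SAP 6 | consent; treated as the protocol indicates (not defined) |
| SAP 2, Protocol 8.6 | the 36 mm device is the treatment; SAP 2 says all subjects received it |
| Protocol 8.11 | consent and implant |
| Protocol 9.7 | eligibility, consent, and procedure and implant per protocol |
| Protocol Table 1, 9.1, 9.2 | population meets the eligibility or inclusion criteria |
| Protocol 9.1 | a subject is a recipient of the product |
| Protocol 10.1 | adverse events are reported for all subjects |

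Eligibility is therefore not peculiar to 9.7; it describes the intended population throughout. Section 8.11 reads as shorthand for the moment of enrolment (signature, then implant) rather than as a rival population. Protocol Table 2 puts the eligibility check and the status form before surgery, so the eligibility condition in 9.7 is normally settled before implantation. No passage tells a site to withhold a number from an implanted subject, or an analyst to remove one.

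**The plan's precision figure**

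Inputs from Protocol 8.4 and SAP 7: S = 0.951, and 170 × 0.80 = 136 at 5 years.

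- Displayed Peto formula: 0.951² × 0.049 / 136 = 0.000326; margin 1.96 × √0.000326 = 3.54%.
- Stated: variance 0.00034, margin 3.6%. The binomial form, 0.951 × 0.049 / 136 = 0.000343, gives 3.63% and matches the stated variance. The gap is at rounding level and does not affect this point.

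**Precision if implanted subjects were left out** (the rates are assumptions; 80% still followed at 5 years; Peto formula)

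| Left out of 170 | n at 5 years | Margin |
|---|---|---|
| 0 | 136.0 | 3.54% |
| 3 (about 2%) | 133.6 | 3.57% |
| 8 (about 5%) | 129.6 | 3.62% |
| 17 (10%) | 122.4 | 3.73% |

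**Shift in the estimate**

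Let f be the fraction left out and r their revision risk relative to those kept. With 4.9% 5-year risk in all implanted subjects, the risk in those kept is 0.049 / (1 − f + f·r), and survival shifts by 0.049 − 0.049 / (1 − f + f·r). For f = 0.05 and r = 5: 0.049 − 0.049/1.20 = 0.0082. Values of f and r are assumptions.

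| f | r = 0.5 | r = 1 | r = 2 | r = 5 |
|---|---|---|---|---|
| 2% | −0.05 points | 0 | +0.10 | +0.36 |
| 5% | −0.13 points | 0 | +0.23 | +0.82 |

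**Kaplan-Meier illustration near 95.1%** (assumed: 170 implanted, 34 censored evenly over 5 years, 8 evenly spaced revisions)

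- All kept: 94.7%.
- One revised subject dropped: 95.3% to 95.4%, depending on which one.
- One revised and four unrevised dropped: 95.2% to 95.3%.
- Five unrevised dropped: 94.6%.

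Over 4 to 12 revisions, dropping one revised subject crosses exp(−0.05) = 95.12% at one count for each timing: 8 if evenly spaced, 9 if all in year 1, 7 if all in year 5. Across all these cases the shift is 0.55 to 0.71 points.

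**The case for a change.** The best case for a change is that the set behind the primary estimate should have one written meaning, and that writing it costs one sentence. If the benign reading is intended, the sentence merely records it; if not, it stops deviating subjects from disappearing from safety and survivorship results alike. SAP section 6 does not say implanted and does not refer to section 2, and the 80% follow-up commitment is also counted in enrolled subjects.

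Part of this stands. The phrase is undefined and the enrolment wordings differ. A sentence naming all consented, implanted subjects, with deviation counts in the SAP 8.2 disposition summary, would be harmless.

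The rest does not carry the point further. Aligning 9.7 with 8.11 alone would leave Table 1, 9.1 and 9.2 still conditioned on eligibility, so it would not give one meaning. The SAP describes treatment in the past tense; a protocol edit now could not recover data on anyone never enrolled. Nor is keeping every stem deviation plainly the better choice: under Protocol 8.2, removal of any component counts as a revision, so failure of a stem outside the permitted list would count against the 36 mm system.

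**Conclusion.** No change is called for. The gap is one of drafting, and analysts would fill it with the set that the rest of the text describes: all consented subjects who received the 36 mm device. The planned 170 and 136 stay as they are.

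The documents show no effect on the 5-year estimate. Under assumed exclusions of 2% to 5% and risk ratios of 0.5 to 5, the shift runs from −0.13 to +0.82 points. Its sign is unknown, and even the largest value is under a quarter of the planned 3.6-point margin (0.82 / 3.6 = 0.23). Crossing 95.1% by losing one revised subject needs one particular revision count for each event timing. SAP section 5 states that there are no hypotheses and that all analyses are exploratory, so no formal test depends on such a crossing.

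This rests on the natural reading of SAP section 6, and on sites having numbered every consented patient whom they implanted. Nothing in either document points the other way.
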